6.2.1 Submission of H&E stained prostate biopsy slides (required for all patients)

Pathology specimens will be collected with a minimum of 10 tissue cores obtained utilizing a standard, extended biopsy pattern for confirmation of prostate pathology. Prostate biopsy slides will be submitted at baseline and 24 months.

Additional biopsies: If, at the discretion of the treating physician, a patient undergoes additional prostate biopsies at a time other than 24 months, the prostate biopsy slides from these additional prostate biopsies should be submitted as well.

Representative stained hematoxylin and eosin (H&E) diagnostic slides from each biopsy site/container are to be submitted to the Alliance Biorepository at Ohio State University for review. The pre-registration sample should be from the initial biopsy showing diagnosis of cancer. Submission of paraffin embedded tissue blocks is not required. Submission of the local pathology report is required. The local pathology report should contain the number of cores obtained for each biopsy to allow central verification that ≥ 10 cores were obtained for each biopsy.

Biopsy slides will be reviewed by [REDACTED]. The Alliance Biorepository at Ohio State University will scan the slides and upload the images to a website and [REDACTED] will review the scanned images. She will forward her evaluation to the Alliance Statistics and Data Center.

If H&E stained slides are not available for submission, digital images may be submitted. Please contact [REDACTED] for further instructions.

6.2.2 Plasma samples (required for all patients)

Throughout all stages of blood processing, shipping, and handling, it is very important to prevent prolonged exposure of samples and separated blood components to light. Work quickly and efficiently. When samples and sample components must be set aside, cover them or put them away from light.

First prepare the vacutainer tubes for protection from light by wrapping aluminum foil around the tube prior to filling it or putting it in a red or amber colored specimen bag.

Draw 10 mL of whole blood in a green top (heparin coagulant) tube and gently invert it once or twice to mix the additive with the blood. Immediately replace the tube into the previously prepared aluminum foil slip or place it into the red or amber colored specimen bag.

Samples should be processed within 30 minutes of collection. If this is not possible, the tube(s) should be refrigerated until centrifugation. Before centrifugation, make sure the brake is off, the speed is set between 2,800 – 3,000 rpm, the temperature is 4° to 8° C and the centrifugation time is set at 10 minutes.

After centrifuging for 10 minutes, allow the centrifuge to come to a complete stop before opening the cover. Do not use the brake as it may cause the red blood cells to become re-suspended in the plasma. Any tube containing red blood cells in the plasma should be re-centrifuged. Immediately return the tubes to the light protection device (aluminum foil pouch or red or amber bag).

The plasma should be aliquotted into cryovials* within 15 minutes after centrifuging. All plasma samples will be pipetted as 0.8 mL amounts into the cryogenic storage vials. Place the samples in the -70°C freezer as soon as possible after aliquotting. Samples must be frozen at least 2 hours before packing them for shipment. If a -70° C freezer is not available, the cryovials can be stored in a -20°C freezer immediately after aliquotting, and then transferred to a -70° C freezer as soon as possible, but for no longer than 2 days (over the weekend). Placing the samples on wet ice or dry ice does not sufficiently preserve the sample; at least a -20° C freezer is required. Samples may NOT be thawed after freezing. See Section 6.2.4 for packing and shipping instructions.

* Cryovial Choices: Some examples of acceptable 2.0 ml cryovials are: Nalgene (Cat #5012-0020), Fisher (Cat #05-669-57), Corning (Cat #430488), VWR (Cat #16001-102).

6.2.3 Serum samples (required for patients enrolled to substudy 151105)

Throughout all stages of blood processing, shipping, and handling, it is very important to prevent prolonged exposure of samples and separated blood components to light. Work quickly and efficiently. When samples and sample components must be set aside, cover them or put them away from light.

First prepare the vacutainer tubes for protection from light by wrapping aluminum foil around the tube prior to filling it or putting it in a red or amber colored specimen bag.

Draw 10 mL of whole blood in a red top tube and gently invert 5 times to mix clot activator with blood. Let blood clot for 30 minutes. Observe a dense clot. Immediately replace the tube into the previously prepared aluminum foil slip or place it into the red or amber colored specimen bag.

Samples should be processed within 30 minutes of collection. If this is not possible, the tube(s) should be refrigerated until centrifugation. Before centrifugation, make sure the brake is off, the speed is set between 2,800 – 3,000 rpm, the temperature is 4° to 8° C and the centrifugation time is set at 10 minutes.

Before you start the centrifugation, make sure the brake is off, the speed is set between 2,800 - 3,000 rpm, the temperature is 4-degrees C to 8-degrees C and the centrifugation time is set at 10 minutes.

After centrifuging for 10 minutes, allow the centrifuge to come to a complete stop before opening the cover. Do not use the brake as it may cause the red blood cells to become re-suspended in the serum. Any tube containing red blood cells in the serum should be re-centrifuged. Immediately return the tubes to the light protection device (aluminum foil pouch or red or amber bag).

The serum should be aliquotted into cryovials* within 15 minutes after centrifuging. All serum samples will be pipetted as 0.8 mL amounts into the cryogenic storage vials. Place the samples in the -70°C freezer as soon as possible after aliquotting. Samples must be frozen at least 2 hours before packing them for shipment. If a -70° C freezer is not available, the cryovials can be stored in a -20°C freezer immediately after aliquotting, and then transferred to a -70°C freezer as soon as possible, but for no longer than 2 days (over the weekend). Placing the samples on wet ice or dry ice does not sufficiently preserve the sample; at least a -20°C freezer is required. Samples may NOT be thawed after freezing. See Section 6.2.4 for packing and shipping instructions.

- * Cryovial Choices: Some examples of acceptable 2.0 ml cryovials are: Nalgene (Cat #5012-0020), Fisher (Cat #05-669-57), Corning (Cat #430488), VWR (Cat #16001-102).

6.2.4 Packing and shipping instructions for plasma and serum samples

- (1) Place dry ice nuggets on the bottom of the insulated shipping container.
- (2) Place each freezer box in a sealed plastic bag. Remove as much air as possible from the bag before sealing.
- (3) Place the sealed bags in the insulated shipping container on top of the dry ice.
- (4) Layer additional* dry ice on top of and around the plastic bags. Place any remaining freezer boxes in sealed plastic bags on top of the dry ice.
 - * Overnight deliveries should contain about 10-12 pounds of dry ice. This will allow the package to remain frozen for 48 hours in case the shipment is delayed.
- (5) Seal the shipping fiberboard box tightly and tape all seams with waterproof tape. To delay thawing, place the box in the -70° C freezer to await pickup. This step need not be done if the box is packed within 2-3 hours of pickup.

Ship specimens to:

Alliance Biorepository at Ohio State University
The Ohio State University
Innovation Centre

Shipment on Monday through Friday by overnight service to assure receipt is encouraged. If shipping on Friday, FedEx or UPS must be used and the air bill must be marked “For Saturday delivery.” Do not ship specimens on Saturdays.

6.2.5 Whole blood (required for patients enrolled to substudy 151105)

Draw 10 mL whole blood in a lavender top (EDTA coagulant) tube and keep refrigerated until shipped overnight to the Alliance Biorepository at Ohio State University. Label the tube with the patient’s initials, patient study ID number, study number (CALGB 70807), and date of collection. The sample should be shipped the same day on a cold pack by overnight mail to:

Alliance Biorepository at Ohio State University
The Ohio State University
Innovation Centre

Shipment on Monday through Friday by overnight service to assure receipt is encouraged. If shipping on Friday, FedEx or UPS must be used and the air bill must be marked “For Saturday delivery.” Do not ship specimens on Saturdays.

6.2.6 Submission of unstained diagnostic prostate biopsy slides (required for patients enrolled to substudy 151105)

Submit ten, or as many slides as contain cancer, 5 µm unstained sections on charged glass slides from the formalin-fixed, paraffin-embedded, diagnostic prostate biopsy blocks to the Alliance Biorepository at The Ohio State University (see Section 6.2). Label the slides with patient study ID number, accession number, and order of sections.

7.0 REQUIRED DATA

Guidelines for Pre-Study Testing

To be completed within 3 months before preregistration

- Baseline PSA, history and physical, DRE

To be completed within 24 months before preregistration

- Prostate Biopsy

	Preregistration	Run-in	Month*							
			3	6	9	12	15	18	21	24
Test and Observations										
History and Physical	X			X		X		X		X
Height†	X									
Weight†	X			X		X		X		X
DRE	X					PRN				PRN
Diet Recall		A				A				A
Labs and Staging										
PSA	X		X	X	X	X	X	X	X	X
QOL Instruments										
Personal Habits Questionnaire	B									
MAX-PC	B			X		X		X		X
Nutritional Self-Efficacy	B			D		D		D		D
I-PSS	B			X		X		X		X
EPIC-26	B			X		X		X		X
FACT-P	B			X		X		X		X
MEAL Counseling Evaluation						D				D
Sample Submission										
Plasma for Carotenoid Analysis	C					X				X
H & E biopsy slides‡	C									X(1)
Correlative Study	See Section 6.2.									
Serum										
Whole Blood										
Unstained Slides‡										

A To be conducted by UCSD staff.

B To be administered to all patients at the pre-registration visit and submitted after the patient is registered to the study.

C To be collected for all patients at the pre-registration visit and submitted after the patient is registered to the study.

D To be administered to patients randomized to Arm A only.

* Clinic visits may be done within +/- 2 weeks of the scheduled 3-, 6-, 9-, etc. month visit. These visits are to be scheduled from the date of randomization.

† Refer to Section 8.1 for height and weight measurement instructions.

‡ Slides should be from the initial biopsy showing diagnosis of cancer.

1 24-month biopsy is not required for patients who have started definitive treatment (e.g., prostatectomy or radiation therapy).

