6.0 DATA SUBMISSION AND SAMPLE SUBMISSION

6.1 Data Submission

Forms should be submitted to the Alliance Statistics and Data Center (SDC) in compliance with the Data Submission Schedule below.

Forms must be submitted electronically using the “Submit to CALGB” button located at the bottom of the last page of each form. Any required forms, supporting documentation or amended forms that cannot be submitted electronically should be mailed directly to the Alliance Data Center for scanning and quality review at the address below:

Alliance Data Center

[Redacted address information]

For the most up-to-date forms, please visit the Alliance or CTSU web site.

Data Submission Schedule:

Form		Submission Schedule
	Pre-Registration Pre-Registration Worksheet	Submit at pre-registration
C-2010	MEAL Participant Contact Information Form	Submit to UCSD staff (See Sec. 5.2)
	Registration Registration Worksheet CALGB 70807 On Study Form	Submit within 2 weeks of registration
C-2002	CALGB 70807 Personal Habits Questionnaire	To be administered to patients at the pre-registration visit and submitted to the Alliance Statistics and Data Center within 2 weeks of registration.
C-2003	CALGB 70807 MAX-PC Form	
C-2004	CALGB 70807 Nutritional Self Efficacy Form	
C-2005	CALGB 70807 IPSS Form	
C-2023	CALGB 70807 EPIC-26 Form	
C-2007	CALGB 70807 FACT-P Form	
	During Intervention	
C-2013	CALGB 70807 Follow Up Form	Submit at 3, 6, 9, 12, 15, 18, 21, 24 months
C-2081	CALGB 70807 PSA Doubling Time Form	Submit at 6 months
C-2003	CALGB 70807 MAX-PC Form	Submit at 6, 12, 18 and 24 months
C-2005	CALGB 70807 I-PSS Form	
C-2023	CALGB 70807 EPIC-26 Form	
C-2007	CALGB 70807 FACT-P Form	
C-2004	CALGB 70807 Nutritional Self Efficacy Form	
C-2008	CALGB 70807 MEAL Study Counseling Evaluation Form	Arm A patients only: Submit at 12 and 24 months
	Post Intervention Follow-Up	
C-2013	CALGB 70807 Follow Up Form	Submit every 3 months until 2 years from date of registration (see Section 8.7)
	Other	
C-260	CALGB Remarks Addenda	Submit as needed

If a study participant chooses to withdraw from the study, submit the C-260 CALGB Remarks Addenda to the Alliance Data Center and copy by fax [REDACTED]

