Seven quality of life measures will be used: Personal Habits Questionnaire will be completed at pre-registration only, the Functional Assessment of Cancer Therapy Scale-Prostate (FACT-P); Memorial Anxiety Scale for Prostate Cancer (Max-PC); International Prostate Symptom Score (IPSS); Expanded Prostate Cancer Index Composite 26 (EPIC-26); and the Nutrition Self-Efficacy will be completed at preregistration and every 6 months. Finally, the MEAL Study Counseling Evaluation Form will be completed at 12 and 24 months (see Section 9.0).

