9.6 Nutrition Self-Efficacy Scale

The Nutrition Self-Efficacy scale assesses the degree to which individuals are confident that they can control their nutrition (79). The scale assesses perceived self-efficacy, the confidence in one's ability to meet one's goals, and coping self-efficacy, defined as optimistic beliefs about one's capability to deal with barriers that arise in plans. The scale consists of 5 items rated on a 5 point Likert scale, ranging from 'very confident' to 'not confident at all'. Internal consistency was excellent (alpha coefficient = .87, n= 1,722). Evidence of validity was provided by the Nutritional Efficacy Scale correlating significantly with nutritional behavior ($r = .34$, $p < .01$) (80). Because quality of life or anxiety has not been formally evaluated in an AS population or in the setting of a randomized clinical trial among AS patients, a battery of scores will be assessed as exploratory variables, with scores at each time point and changes in scores over time assessed between the intervention and control groups using student's t-test and linear regression modeling.

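### The Section 7.0 calendar limits Nutrition Self-Efficacy after baseline to Arm A, while Section 6.1 sets no arm limit and Section 9.6 plans a between-arm comparison that would then lack control data

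*Combined protocol and SAP*

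**What the plan says.** Four places in the protocol govern this scale.

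- **Section 7.0, calendar.** The row "Nutritional Self-Efficacy" is coded B at preregistration and D at months 6, 12, 18 and 24. Footnote B reads "To be administered to all patients at the pre-registration visit and submitted after the patient is registered to the study". Footnote D reads "To be administered to patients randomized to Arm A only". MAX-PC, I-PSS, EPIC-26 and FACT-P carry a plain X at the same four visits. The only other row coded D is the MEAL Counseling Evaluation.
- **Section 6.1, Data Submission Schedule.** Under the intervention period, form C-2004 ("CALGB 70807 Nutritional Self Efficacy Form") is grouped with those four instruments, and the group's schedule is "Submit at 6, 12, 18 and 24 months". The next form, C-2008 (the counseling evaluation), carries an explicit limit: "Arm A patients only: Submit at 12 and 24 months".
- **Section 8.4, Quality of Life Instruments.** The scale ends a list that also contains FACT-P, MAX-PC, IPSS and EPIC-26: "and the Nutrition Self-Efficacy will be completed at preregistration and every 6 months". No arm is named.
- **Section 9.6, the scale's own section.** It closes by planning, as exploratory work, a comparison of a set of scores at each time point, with "changes in scores over time assessed between the intervention and control groups", by t-test and linear regression. Section 9.0 counts this scale among the seven quality of life measures.

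**The concern.** The calendar is the table that sites are likely to use in deciding what to hand to which patient at which visit. Read literally, it leaves the control arm with one self-efficacy score per man, taken before randomization. The comparison in Section 9.6 needs scores from both arms after randomization, and no analysis method can restore data that were never collected.

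The scale also has a place in the protocol's reasoning. Section 1.5 treats self-efficacy as a central element of the behavioral theory behind the programme and expects it to contribute to quality of life. Section 8.6 has counselors watch for its decline. With follow-up in Arm A alone, a change in score cannot be separated from a time trend, regression to the mean or the effect of repeated questioning. Control scores cannot be assumed flat either, because control men receive the nutrition booklet (Section 8.3), quarterly newsletters (Section 8.3) and dietary recall calls (Section 8.5).

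**Working it through.** The documents give no sample size, standard deviation or power for this scale, so there is no stated figure to reproduce. The check is a comparison of sections followed by a count of forms.

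**Step 1: sections side by side, months 6 to 24**

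| Section | Role | Arm B after baseline |
|---|---|---|
| 7.0 | visit calendar | excluded by footnote D |
| 6.1 | form submission | not excluded; the limit is written on the next form only |
| 8.4 | visit description | no arm stated |
| 9.6 | analysis | needed for the comparison |

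Section 7.0 and Section 9.6 cannot both be carried out for this scale. Section 6.1, as the table reads, supports collection in both arms: its authors wrote an arm limit where they wanted one and put none on C-2004. Section 8.4 adds little, for a reason given under the objection.

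**Step 2: forms planned**

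Inputs: 464 patients, 232 per arm (Section 11.1); one baseline assessment in both arms and four later visits (Section 7.0).

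- Post-baseline forms per arm if collected: 232 x 4 = 928.
- Under the calendar: 928 in Arm A, 232 x 0 = 0 in Arm B.
- Both arms, post-baseline: 2 x 928 = 1,856. Share not collected: 928 / 1,856 = 50%.
- Both arms, all five occasions: 464 x 5 = 2,320. Share not collected: 928 / 2,320 = 40%.

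These counts are before dropout. As an illustration, with half of the 418 patients in the Section 11.2 calculation (209 per arm), the control forms not collected would be 209 x 4 = 836.

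**Step 3: what can be estimated**

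Under the calendar, two things remain: a between-arm comparison at baseline, and a within-arm change in Arm A. Neither is the post-baseline comparison in Section 9.6.

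For scale only, suppose the form is collected in both arms and assume a two-sided 5% test with 80% power at one visit. The detectable difference is (1.960 + 0.842) x sqrt(2/n) standard deviations. With n = 232 per arm this is 0.26; with n = 209 it is 0.27. With no control data after baseline there is no estimate at all, so the issue is not one of precision.

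**The case against.** **Arm A only may be deliberate.** Code D stands in all four follow-up cells of the row while its neighbors carry X, which does not look like a slip. The scale measures confidence in controlling one's nutrition and meeting one's goals, and only Arm A is given dietary targets and counseling. This stands: the documents do not show that footnote D is the error. It does not remove the conflict with Sections 6.1 and 9.6.

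**Section 8.4 is weak evidence.** It also names no arm for the MEAL Counseling Evaluation, which Sections 6.1, 7.0 and 9.7 confine to Arm A. Silence there does not mean both arms. This stands.

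**The Section 6.1 table was read from a PDF.** During the intervention period C-2004 is listed last in its group, directly above C-2008, and a limit could have been lost with the cell layout. This is possible and cannot be settled from the text. As it reads, the limit belongs to C-2008.

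**Section 9.6 does not name this scale as a compared score.** Its sentence starts from quality of life and anxiety. The Section 9.0 list also includes the baseline-only Personal Habits Questionnaire and the Arm A satisfaction form, so being on that list does not by itself imply a follow-up comparison. Section 11.3 does not name self-efficacy. This weakens the inference, but the sentence sits in the scale's own section and its natural reading includes the scale.

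**Stronger readings to avoid.** A reader might infer that Sections 6.1, 8.4 and 9.6 all require the scale in every man and all compare the arms. They do not: only Section 9.6 compares arms, and no section states that all men complete the scale after baseline. A reader might also infer that the comparison is certain to be lost. That depends on sites following the calendar; sites working from Section 6.1 would collect control forms.

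**Conclusion.** The inconsistency is real and should be corrected. If the calendar is followed, Arm B has no self-efficacy scores after baseline, and the exploratory comparison in Section 9.6 cannot be made for this scale at months 6, 12, 18 or 24. If practice varies between sites, control data will exist only where a site happened to follow Section 6.1, and a comparison based on them would depend on which sites those were.

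The conclusion rests on three assumptions: that sites act on the calendar, that the Section 6.1 table is arranged as it reads, and that the Section 9.6 comparison includes the scale described in that section.

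The reach is limited. The analysis is exploratory, and no mediation analysis of self-efficacy is planned. The primary endpoint does not use this scale. The anxiety and health-related quality of life objectives rely on instruments that the calendar schedules in both arms. A reader might infer that those objectives are compromised; nothing in the documents supports that.

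**What to change.** Reconcile Sections 6.1, 7.0, 8.4 and 9.6 so that they give one schedule for this scale.

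**Preferred:** in the Section 7.0 calendar, replace D with X for Nutritional Self-Efficacy at months 6, 12, 18 and 24, and keep D for the MEAL Counseling Evaluation only. State in Section 8.4 that both arms complete the scale. This makes the Section 9.6 comparison possible. The cost is a calendar edit and a 5-item form for control men at four visits where they already complete MAX-PC, I-PSS, EPIC-26 and FACT-P.

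**If follow-up in Arm A only was intended:** mark C-2004 as Arm A only after baseline in Sections 6.1 and 8.4, and remove this scale from the post-baseline between-arm comparison in Section 9.6. This adds no data collection but gives up the randomized comparison, leaving only a description of change within Arm A.

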8.0 INTERVENTION

The principal strategy to promote dietary change in the intervention arm will be a telephone counseling protocol with individualized, one-on-one assistance tailored to each participant. The intervention will last 24 months. Intervention participants will engage in a series of telephone-based diet counseling sessions throughout the study. The first phase of sessions will guide initial diet-change attempts, the second will help participants complete their diet changes, and the third and fourth phases will enable participants to maintain and monitor their diet changes. This highly structured, computer-assisted telephone counseling protocol will facilitate standardization of the intervention.

